The *objectives* of this project are to:

- determine the symptoms and lung function characteristics and course of asthma exacerbations in patients with severe asthma
- (ii) evaluate the role of infective agents (respiratory viruses and bacteria)

3

- (iii) define the biomarkers in exhaled breath, sputum and in blood
- (iv) study the presence of oxidative stress, phagocytic capacity of macrophages and corticosteroid insensitivity.

Major outcomes of this study will be (i) to assess the feasibility of diagnosing exacerbations earlier (ii) to determine the heterogeneity of the presentation and course of exacerbations (iii) to identify exacerbation phenotypes in terms of causes and (iv) to look for potential targets for treatment.

Study design

We have a database of 300 current patients with severe asthma defined according to ATS criteria(1) with exacerbation rate of 1.5 ± 2.8 (SD)/year. To achieve 1.7 exacerbations after 16 weeks will require 36 patients at 90% power and 5% significance. Adjusting for a possible dropout of 30% would require 56 patients. Therefore, 60 patients will be recruited. To be on the safe side, we will enrol patients with a history of \geq 3 exacerbations/year for a prospective observational study.

At entry Visit 1, we will enrol and characterise these patients. They will be observed over 12 months during which the number of exacerbations will be recorded on the basis of objective measures with evaluation of ACQ and daily morning and evening PEF. At the earliest onset of each exacerbation, the patient will be requested to contact by phone the Asthma BRU Unit. For one of these events, patients will be asked to attend the laboratory for a series of tests at Visit 2 similar to Visit 1. Visit 3 will be planned within 14 days after Visit 2, when the patient has recovered.

In 30 of the 60 patients, we will request for an additional attendance of a subsequent exacerbation (Visit 4) with follow-up (Visit 5). For other exacerbations not studied, the patient will be asked to keep a detailed diary record of symptoms with severity scoring and spirometric and PEF measurements (Exacerbation Diary) over a period of 2 weeks after the onset of exacerbation.

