Patients will have their exacerbations treated in the usual way. The only exception will be the use of antibiotics which will be withheld and initiated (if indicated) after the patients has been through Visit 2. Those who have to be hospitalised will not be studied, and only those who can attend the Clinical Research Unit will be studied. The more severe exacerbations will therefore be missed but will be recorded in the patient's diary.

Tests to be performed Visits 1, 2 and 3:

1. Diary of symptom scores, use of beta-agonist reliever and other treatments for 2 weeks

- 2. PEFR and spirometry twice daily for 2 weeks
- 3. Markers of systemic inflammation in blood: CRP, IL-8, IL-6, together with Meso-Scale-Discovery (MSD) platform for other cytokines.
- 4. Markers of oxidative stress in blood, exhaled breath condensate (EBC) and urine: malondialdehyde (MDA) and 8-isoprostanes (31).
- Nitric oxide (NO) levels in exhaled breath measured twice daily for 2 weeks using a portable hand-held NO meter (NO_{breath}). EBC for pH & free iron (32)
- 6. Induced or spontaneous sputum for inflammatory cells and assays of cytokines in supernatants using Meso-Scale-Discovery (MSD) platform, bacteriological culture and for microbiome analysis. H₂S which is elevated in asthma in relation to sputum neutrophil counts (33)will also be measured. If spontaneous sputum is not available, sputum will be induced using ultrasonic nebulization of isotonic saline (34), which is safe in patients during an exacerbation (35).
- 7. Sputum for bacteriological culture and colony forming units.
- 8. PCR for respiratory viruses from nasopharyngeal swabs and sputum RNA and reverse transcription performed for respiratory viruses including rhinovirus, influenza virus types A and B, parainfluenza viruses 1 to 3, coronaviruses and respiratory syncytial virus types A and B, and Chlamydia pneumonia, and Mycoplasma pneumonia using real-time 'TaqMan' assays in collaboration with [name], NHLI.
- Sputum microbiome: 16S rRNA PCR and pyrosequencing will be performed on sputum with amplification of the V3-V5 regions (36) in collaboration with Professors [name] and [name], NHLI.
- 10. Studies on blood cells:
 - MDM's phagocytosis of fluorescently-labelled Pseudomonas aeruginosa and Staphylococcus aureus ([name], NHLI) on macrophage-derived monocytes as described previously (37)
 - (ii) Transcriptomic analysis of blood CD4⁺ and CD8⁺ T-cells and monocytes, as previously described (14)

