 - Studies of corticosteroid insensitivity in peripheral blood mononuclear cells and in whole blood ([name], NHLI) (38)

Definition of exacerbation and monitoring

Because these patients with severe asthma are usually well-experienced 'exacerbators', they will be asked to 'diagnose' their own exacerbations. Each has an individualised way of recognising an

exacerbation. We will discuss with each patient t their way of recognising a deterioration and try and work out whether earlier signal warning is possible. One of our aims is to find out what the objective measures of deterioration are. We will also ask patients to record their symptoms and lung function as soon as they feel the onset of an exacerbation, since exacerbations are recognised by the patient as events that are 'clinically identified by being outside the patient's usual range of day-to-day asthma variation'(5). They will also contact the Study Coordinator (Nurse or Clinical Research Fellow) to determine if they can attend for Visit 2. The patient will receive or administer treatments for the exacerbation as usual without interference from the Research team. Except for the exacerbation that will be studied (Visit 2 or Visit 4), the patient will be requested to refrain from starting any antibiotic therapies, which will be started (if this has been prescribed) as soon as Visit 2 studies have been completed.

Data analysis

- The daily variation of symptoms and lung function during the exacerbation visits (2 and 4) will be analysed, and related to the changes observed in the various parameters collected at exacerbation. Comparison of these biomarkers to those at Visit 1 and at the recovery visit will allow for ascertainment of biomarkers that may be associated with exacerbations. Bacterial- or virusassociated, or eosinophil- or neutrophil-associated exacerbation will be defined.
- 2. Unbiased mathematical methods such as factor and cluster analyses will be used to identify factors at exacerbations and classify groups of similar characteristics looking at all the data collected including the transcriptomic and cytokine profile data. The analysis will be performed by the Bioinformatics group led by [name] of Discovery Science at Imperial College.
- 3. The stability of the exacerbation profile will be examined within the 30 patients who have had a repeat exacerbation visit. We could also look at this small group as a validation data set.

Timelines and milestones

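### The 30 repeat patients offered as a possible validation set come from the same 60 discovery patients, with a shared Visit 1 and no stated hold-out; they can show within-patient repeatability, not independent validation

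*Combined protocol and SAP*

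**What the plan says.** Study design fixes who the patients are: "In 30 of the 60 patients, we will request for an additional attendance of a subsequent exacerbation" (Visit 4), with a follow-up (Visit 5). Visit 1 takes place once, at entry; no second baseline precedes Visit 4.

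Data analysis then has three items.

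- Item 1 looks for exacerbation biomarkers by "Comparison of these biomarkers to those at Visit 1 and at the recovery visit". It does not say whether both comparators are required, or which recovery visit serves Visit 4. It names Visits 2 and 4 together when it describes the analysis of daily symptoms and lung function.
- Item 2 runs factor and cluster analyses, "looking at all the data collected including the transcriptomic and cytokine profile data".
- Item 3 gives the repeat group a committed use, "The stability of the exacerbation profile will be examined within the 30 patients who have had a repeat exacerbation visit", and then a tentative one, "We could also look at this small group as a validation data set".

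No section states a hold-out, a locked marker list, a comparator or a success rule for that second use. Timelines and milestones lists biomarker validation for January to September 2016 without naming the data. Future plans of research, item 2, assigns validation of some biomarkers to later multicentre studies.

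**The concern.** A validation set should be able to contradict the discovery result. These 30 patients can do so only in part, for three reasons.

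1. **Shared baseline.** A Visit 1 mean that is low by chance makes Visit 2 look raised, and makes Visit 4 look raised as well.
2. **Possible reuse.** If Visit 4 helps to select a marker, it cannot then test that marker fairly.
3. **Same people.** Traits that persist in a patient recur at a second event whether or not a marker or cluster means anything for exacerbations in general.

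Biomarkers and exacerbation phenotypes are among the study's stated objectives and major outcomes. The risk is that recurrence in the same people is reported as validation of them.

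**Working it through.** **Plan's own figure.** There is none on this point: no power, threshold or success rule is given for the validation use. The sample-size figures (36, 56, 60) concern exacerbation counts and are not used below, except for the 30% dropout.

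**Inputs from the documents.** 60 discovery patients, 30 repeated, one Visit 1 each. With the plan's 30% dropout ("Adjusting for a possible dropout of 30% would require 56 patients") falling equally on both groups, 60 × 0.7 = 42 and 30 × 0.7 = 21.

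**Assumptions, not in the documents.** The marker has no true effect. Visits have equal variance (set to 1) and independent noise after removal of each patient's own level. A finding is two-sided p<0.05, and it repeats if it has the same direction and p<0.05 in the 30.

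**Formula.** With r the correlation between the discovery and repeat test statistics, the repeat rate is P(Z_rep > 1.96 | Z_disc > 1.96) under a bivariate normal. At r = 0 this is 2.5%, the benchmark for independent patients.

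*Visit 4 held out, against the shared Visit 1.* Within a patient, V2−V1 and V4−V1 each have variance 2 and covariance 1, so their correlation is 0.5. Then r = 0.5 × √(30/60) = 0.354, and the rate is **11.5%**. For 42/21 the ratio is still one half, so r and the rate are unchanged. A t-test simulation gave 11.8% (60/30) and 10.8% (42/21).

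*Visit 4 held out, against Visit 5.* No measurement is shared, so the rate is **2.5%**. If changes at a patient's two events correlate at rho, r = rho × √(30/60):

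| rho (assumed) | r | repeat rate |
|---|---|---|
| 0 | 0 | 2.5% |
| 0.1 | 0.071 | 3.6% |
| 0.2 | 0.141 | 5.0% |
| 0.3 | 0.212 | 6.8% |

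*Visit 4 pooled into discovery, against Visit 1.* Average Visits 2 and 4 in the repeat patients. Discovery variance is 30 × 1.5 + 30 × 2 = 105, repeat variance is 30 × 2 = 60, and covariance is 30 × 1.5 = 45. So r = 45/√(105 × 60) = 0.567, and the rate is **22.6%**. With each exacerbation as its own row (standard error allowing for repeats), discovery variance is 30 × 6 + 30 × 2 = 240 and covariance is 30 × 3 = 90. So r = 90/√(240 × 60) = 0.75, and the rate is 38.1%.

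*Visit 4 pooled, against Visit 5.* Discovery on V2−V3, averaged with V4−V5 in the repeat patients, has variance 30 × 1 + 30 × 2 = 90 and covariance 30 × 1 = 30. So r = 30/√(90 × 60) = 0.408, and the rate is 13.8%. Changing the comparator does not replace the hold-out.

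**Clusters.** Data with no true clusters were simulated: k-means on 60 patients at Visit 2, k = 2 or 3, 5 or 10 structureless normal markers, and 30 Visit 4 records assigned to the nearest Visit 2 centroid. Label agreement between the visits was significant in this share of simulated studies:

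| within-patient correlation (assumed) | significant agreement |
|---|---|
| 0 | 2–4% |
| 0.1 | 6–12% |
| 0.3 | 23–42% |
| 0.5 | 62–88% |

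The edges are soft: a separately coded run gave 24–52% at 0.3. The direction is clear: agreement rises with patient stability although no cluster exists.

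**The case against.** The strongest reply is that little rests on the sentence. It says only that the group could be looked at in this way, after a sound committed use. Future plans of research sends validation of some biomarkers to multicentre studies and examines monitoring tools in newly recruited patients. That stands, and it limits the weight.

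Secondly, a reader might infer that the plan pools Visit 4 into discovery, because item 2 speaks of all the data collected. The documents do not support that. The phrase goes on to name kinds of data, so it may describe data types rather than visits, and calling a group a validation set can itself imply separation. Item 1 names Visits 2 and 4 together, but for daily symptoms and lung function. The text neither states pooling nor excludes it, so the pooled figures are conditional.

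Thirdly, item 1 taken literally may require both comparators. Simulated at both steps, that gives a repeat rate of about 1.0%, below 2.5% but about double the 0.5% expected in independent patients under the same rule.

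Lastly, Visit 5 is not a clean comparator. It is a follow-up with no stated timing, it comes after usual treatment, and the list of tests is headed for Visits 1, 2 and 3 only. This stands, and is why the fix does not rest on Visit 5 alone.

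**Conclusion.** The point holds in a limited form. The 30 patients are not an independent sample, and nothing written keeps their second event out of marker selection or cluster derivation. They support a statement about repeatability within patients.

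On the stated assumptions, a chance finding repeats about 11.5% of the time against the shared Visit 1 with Visit 4 held out, and about 23% or more if Visit 4 is also pooled, compared with 2.5%. With Visit 4 held out and Visit 5 as comparator there is no inflation without a persistent patient response, and 3.6–6.8% at assumed correlations of 0.1–0.3. The cluster effect cannot be sized for this study, because the documents give no within-patient correlation.

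Three stronger readings should be avoided. The first is that any repeat in these patients is spurious: a held-out Visit 4 against Visit 5 is a fair test against visit noise, though not a test in new patients. The second is that the 2016 milestone is compromised: its data are not named, so the point reaches it only if these 30 are used. The third is that bacterial labels will repeat merely through carriage. Causes of exacerbations does report about half of sputum cultures positive in stable patients, but the rule for the cause labels is not given, and the planned colony counts would allow one based on change.

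This should be changed, mainly in wording; it does not undermine the study.

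**What to change.** - In Data analysis item 3, replace the validation wording with within-patient repeatability: an ICC for biomarkers and kappa for the phenotype label, each with a 95% CI.
- If markers or clusters are checked internally in these patients, fix the marker list and cluster rule without Visits 4 and 5. Alternatively, use cross-validation or bootstrap with all visits of a patient kept together.
- Report the repeat comparison against both Visit 1 and Visit 5, noting that Visit 1 is shared with discovery and that Visit 5 follows usual treatment. Confirm that the listed tests apply at Visits 4 and 5.
- Name the data behind the 2016 biomarker validation, and reserve the term validated for results in separate patients.

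**Cost.** No new patients are needed. Performance estimates become slightly less favourable. A hold-out leaves up to 30 of 60 + 30 = 90 exacerbation profiles (correlated ones) out of clustering. The paired change detectable with 80% power at two-sided 5% is 0.37 SD of the differences if all 60 complete, against 0.368 × √(105/120) = 0.34 SD with Visit 4 averaged in. Repeatability from 30 pairs is imprecise: for an observed ICC of 0.5, tanh(0.549 ± 1.96/√28.5) = tanh(0.549 ± 0.367), a 95% CI of about 0.18 to 0.72.

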Oct 2013-Dec 2013: Setting up of study, identification of patients, setting up methods. Jan 2014-Dec 2014: Recruitment of 30 patients, and follow up to Dec 2014 Jan 2015-Dec 2015: Recruitment of 30 patients, and follow up to Dec 2015 Jan 2016-Sept 2016: Completion of assays, analysis of data, biomarker validation

Future plans of research

 Information obtained from this study will allow us to plan better any future therapeutic studies on asthma exacerbations and will also provide us with an idea of targets for treatments for particular types of exacerbations. Therefore, we plan to use the new information gathered to plan for future studies (eg the number of subjects needed for a therapeutic study).

One target of therapy that we are seeking confirmation for is that of oxidant stress. Currently there are no good antioxidants, but N-acetylcysteine or other similar medications is available and could be tested as treatment for exacerbations. We will also test drugs not only for treating exacerbations, but also for reducing exacerbation rate. This may include approaches to reduce corticosteroid insensitivity since the recurrence of exacerbations in patients taking high dose corticosteroids is a reflection of corticosteroid insensitivity. p38 MAPK inhibitors may be such a drug (39).

- 2. There will be a need for validation of some of the identified biomarkers for each exacerbation phenotype, and this will be done in multicentre studies in collaboration with other Centres within the BTS Severe Asthma Group.
- 3. This research will also provide information about the best tools to monitor exacerbations in severe asthma patients. This will be examined in newly-recruited patients to our cohort.

Reference List

- (1) Proceedings of the ATS workshop on refractory asthma: current understanding, recommendations, and unanswered questions. Am J Respir Crit Care Med 2000 December;162(6):2341-51.

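### Patients are to be observed for 12 months, but the timeline ends each cohort's follow-up in the December of its own recruitment year

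*Combined protocol and SAP*

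**What the plan says.** Study design enrols and characterises patients at Visit 1 and then states: "They will be observed over 12 months during which the number of exacerbations will be recorded". Exacerbations arising in that period supply the study's main data. Visit 2 depends on a first event: "For one of these events, patients will be asked to attend the laboratory for a series of tests". Visit 4 depends on a later one: "In 30 of the 60 patients, we will request for an additional attendance of a subsequent exacerbation".

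Timelines and milestones gives the calendar:

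- October to December 2013: set-up and identification of patients.
- January to December 2014: "Recruitment of 30 patients, and follow up to Dec 2014".
- January to December 2015: "Recruitment of 30 patients, and follow up to Dec 2015".
- January to September 2016: assays, analysis and biomarker validation. No follow-up is listed.

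Data analysis relies on the studied events. The biomarker comparison and the factor and cluster analyses use exacerbation-visit data, and the repeat visits have their own analysis: "The stability of the exacerbation profile will be examined within the 30 patients who have had a repeat exacerbation visit". The plan gives no accrual pattern or last enrolment date, and does not say how unequal follow-up would be handled.

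**The concern.** The two sections give different lengths of observation. If recruitment uses the calendar year allotted to it and follow-up stops that December, a patient enrolled in July is observed for about six months and one enrolled in December for almost none.

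An exacerbation can be studied only if it falls within follow-up, so shorter follow-up reduces three things:

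- the number of patients who can reach Visit 2, on which the biomarker and cluster analyses rest;
- the number who can reach Visit 4, on which the stability analysis rests;
- the meaning of the recorded number of exacerbations, which would not be a 12-month count for most patients.

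The last matters for later use as well: Future plans of research intends to draw on this study when planning later ones, including their sample size.

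**Working it through.** **Calendar arithmetic.** Follow-up is the end of December of the recruitment year minus the enrolment date. If accrual is even over the first W months of the year, mean follow-up is 12 − W/2 months, minimum follow-up is 12 − W months, and total follow-up is 60 × mean/12 patient-years. W is an assumption; the plan gives no value.

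| W (months) | Mean follow-up | Minimum | Patient-years in 60 |
|---|---|---|---|
| 0 | 12 | 12 | 60 |
| 6 | 9 | 6 | 45 |
| 12 | 6 | about 0 | 30 |

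The plan's 12 months is reproduced only at W = 0.

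**Inputs for the sensitivity check.** There are 60 patients. The plan's 30% dropout ("Adjusting for a possible dropout of 30% would require 56 patients") gives 0.30 × 60 = 18 dropouts and 42 completers. Two event-rate assumptions are used.

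1. *Poisson, 3 a year.* This sets the future rate equal to the entry threshold of at least 3 exacerbations a year.
2. *Derived rate.* The database is described "with exacerbation rate of 1.5 ± 2.8 (SD)/year". A negative binomial with that mean and SD has k = 1.5²/(2.8² − 1.5) = 0.355. The probability of 3 or more events in a year is then 0.197, and the mean future rate in such patients is 5.07 a year, assuming each patient's own rate is stable.

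**Formulas.** Under Poisson, P(at least 2 events in t years) = 1 − e^(−3t)(1 + 3t).

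- Full year (t = 1): 1 − 4e^(−3) = 0.801.
- Even recruitment (averaged over t from 0 to 1): 1 − 2(1 − e^(−3))/3 + e^(−3) = 0.416.

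Let P be the probability for a patient who stays, and P′ the probability for one who leaves at a time uniform over their own follow-up. Expected counts are 60P with no dropout, 42P + 18P′ if 18 leave part-way, and 42P if 18 contribute nothing.

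**At least 2 events (Visit 4 possible).** The last column gives no dropout / 18 leaving part-way / 18 contributing nothing.

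| Rate | Recruitment | P | P′ | Expected patients |
|---|---|---|---|---|
| Poisson 3/year | all have 12 months | 0.801 | 0.416 | 48.1 / 41.1 / 33.6 |
| | over 6 months | 0.645 | 0.307 | 38.7 / 32.6 / 27.1 |
| | even over the year | 0.416 | 0.191 | 25.0 / 20.9 / 17.5 |
| Derived, 5.07/year | all have 12 months | 0.826 | 0.521 | 49.6 / 44.1 / 34.7 |
| | over 6 months | 0.730 | 0.427 | 43.8 / 38.4 / 30.7 |
| | even over the year | 0.521 | 0.288 | 31.3 / 27.1 / 21.9 |

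**At least 1 event (Visit 2 possible).**

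| Rate | Recruitment | P | P′ | Expected patients |
|---|---|---|---|---|
| Poisson 3/year | all have 12 months | 0.950 | 0.683 | 57.0 / 52.2 / 39.9 |
| | even over the year | 0.683 | 0.437 | 41.0 / 36.6 / 28.7 |
| Derived, 5.07/year | all have 12 months | 0.937 | 0.729 | 56.2 / 52.5 / 39.4 |
| | even over the year | 0.729 | 0.508 | 43.8 / 39.8 / 30.6 |

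**Where 30 repeat-visit patients stop being expected.** At the derived rate, the longest recruitment window that still gives 30 is the full 12 months with no dropout (31.3), 10.7 months with 18 leaving part-way, and 6.7 months with 18 contributing nothing. At Poisson 3 a year the windows are 9.8, 7.4 and 3.8 months. Under even recruitment at the derived rate, 30 is missed from 3 dropouts contributing nothing (57 × 0.521 = 29.7) or 6 leaving part-way (54 × 0.521 + 6 × 0.288 = 29.9).

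**Can early recruitment be assumed?** The same fit puts 0.197 × 300 = about 59 database patients at 3 or more events a year, against 60 needed.

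All counts are before removing hospitalised or unattended events, so the numbers actually studied would be lower.

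**The case against.** The timeline is a four-line list of milestones, not a visit schedule, and two benign readings exist. First, each January-to-December label may cover recruitment and follow-up together, with patients entering early in the year after identification in late 2013. That is possible, but it is not stated or required. Second, December 2014 may be only a year-end milestone, with the first cohort continuing into 2015. That could remove the shortfall for half the sample, but it does not help the second cohort, for which nothing after December 2015 is listed.

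The consequences can also be called modest, and much of this stands. Data analysis contains no exacerbation-rate comparison, so unequal follow-up affects the recorded count as a descriptor rather than a formal endpoint. The 30 repeat visits are a request, not a powered number, and the plan itself calls the group small. With recruitment completed within 3 months, at least 30 is expected in every rate and dropout scenario used here; the lowest is 42 × 0.735 = 30.9. At the derived rate, even recruitment without dropout still gives 31.

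The modelling has limits too. The entry criterion is a history of exacerbations, so 3 a year is an assumed future rate and not a guaranteed minimum. The figure of 59 rests on a two-moment fit and on recruitment being confined to the current database, which the plan does not say.

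These points bear on the size of the loss. They do not remove the conflict between the two sections.

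**Conclusion.** The concern holds. The inconsistency follows from the printed dates alone: 12 months is the stated observation period but only the maximum that the calendar allows. No wording in the plan reconciles them.

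The size of the loss rests on assumptions about accrual, event rate and dropout timing. Even recruitment would halve total follow-up. Under it, the expected number of repeat-visit patients falls below 30 at both rates once the plan's 30% dropout is applied (17.5 to 27), whereas with a full 12 months it stays above 30 in every scenario shown (34 to 50). With early recruitment the loss is small. This is lost information for the biomarker, cluster and stability analyses, not failure of a statistical criterion. It should be corrected.

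**What to change.** **Preferred route.** State that each patient is followed for 12 months from their own Visit 1. Patients enrolled in 2014 then continue into 2015, the last finishing by December 2015. For the second cohort, give a last enrolment date that fits the September 2016 end. Enrolment to the end of March 2015 would end follow-up in March 2016 and leave 6 of the 9 months set aside for assays and analysis. Enrolment after September 2015 would run past September 2016.

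**If the calendar cannot move.** Change Study design to read 'up to 12 months', and report exacerbation frequency per person-time, for example using a log follow-up offset if a model is fitted. Restate the expected number of repeat-visit patients with the rate, accrual and dropout assumed.

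**Cost.** The fallback needs only a wording change and a person-time denominator. The preferred route makes the cohorts' visits, diaries and assays overlap in 2015, for which the documents give no capacity figure, and carries some follow-up into the 2016 assay period. It also needs second-cohort recruitment fast enough to meet the chosen date; if accrual runs through December 2015, full follow-up would end about December 2016, beyond the planned close. Either route removes the contradiction; neither guarantees 30 repeat visits.
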